8.6.3.3 Safety Laboratory Evaluation

Patient’s safety will be monitored daily at each Visit through laboratory tests. Safety laboratory assessments shall include all parameters for the evaluation of LTLS/CTLS, according to Cairo and Bishop Criteria (see Appendix I: Definition of LTLS and CTLS).

Safety tests will be locally performed in order to ensure prompt patient’s management.

The laboratory print-outs should be identified with the patient number. All print-outs should be dated and signed by the Investigator and filed in the patient’s record. The current valid version of the respective normal ranges as well as any update needs to be notified to the Sponsor. Any out of range value shall be clinically assessed by the Investigator. Safety laboratory results as well as clinical assessments for out of range values will be recorded in eCRF.

The volume of blood to be drawn for each assay will amount to a maximum of 4 ml.

Urinalysis will be performed at Screening, Visit 1, Visit 4, Visit 8 and repeated at Visit 10. Urinalysis test results shall be clinically assessed by the Investigator and the only assessments have to be recorded in eCRF.

Tests are shown in Table 3.

Table 3: Serum, Blood and Urine Sample Analyte Listing

SERUM CHEMISTRY	HEMATOLOGY	URINALYSIS
Creatinine	Haemoglobin	pH
sUA	Haematocrit	Density
Potassium	RBC count	
Phosphorus	Platelet count	
Calcium	WBC count and (absolute and %):	Nitrite
BUN / Urea	neutrophil	Protein
Albumin	lymphocyte	Glucose
Alkaline phosphatase	eosinophil	Ketones
Amylase	basophil	RBC
Glucose	monocytes	WBC
Total protein		Epithelial cells
Total bilirubin and Direct bilirubin		Casts
ALT and AST		Bacteria
LDH		Yeast
GGT		Crystals
INR		
prothrombin time/prothrombin activity		
Sodium		
Chloride		
Beta-HCG (ONLY at Screening if applicable)		
ESTIMATED PARAMETERS		
CLcr calculation according to Cockcroft and Gault formula		

In order to guarantee the proper management of the patient, any additional sampling or examination is allowed anytime, upon Investigator judgment.

8.6.3.4 12 Lead ECG

12 Lead ECG will be performed locally, using standard equipment available at site, at the following Visits: Screening Visit, Visit 3, Visit 8 and Visit 10.

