Protocol Version(s)	Final Version 1.0 dated 12 Apr 2016
Amendment	Protocol Amendment No. 2, dated 03 Feb 2017
Previous Amendment(s)	Protocol Amendment No. 1, dated 02 Feb 2017
Study code	FLO-02
Study Nick Name	FLORET
EudraCT-Number	2016-001445-61
Investigational Medicinal Product	FEBUXOSTAT

The contents of this **Substantial Amendment No. 2 dated 03 Feb 2017** refers to changes made to the **Clinical Trial Protocol Final Version 1.0 dated 12 Apr 2016** and **Amendment No. 1 dated 02 Feb 2017**.

Submission for approval of this Amendment No. 2 will be processed through the Competent Authority, Ethical Committees, and Investigators involved in the study in Hungary.

1. Reasons for the Amendment

Glomerular Filtration Rate (GFR) is usually accepted as the best overall index of kidney function. In clinical practice kidney function is evaluated by measuring the estimated Glomerular Filtration Rate (eGFR) or Creatinine Clearance.

According to the ¹international guidelines published in 2012 by KDIGO (Kidney Disease: Improving Global Outcomes) severe renal insufficiency (grade 4) corresponds to creatinine clearance <30 mL/min. For adult patients this classification is considered as the most appropriate and is the same category considered for the use of Febuxostat as reported in its SmPC.

For the pediatric population a more conservative approach is commonly applied, and it considers the corrected creatinine clearance with the cut off <60 mL/min/1.73 m² as the indicator of kidney damage.

As requested by the Hungarian National Institute of Pharmacy and Nutrition Agency, the exclusion of adult and paediatric patients with severe renal function will be based on the cut off of the clearance creatinine < 30 mL/min and < 60 mL/min/1.73 m², respectively. Therefore, the criteria relative to kidney function making the patients eligible to take part to the study as well as for treatment withdrawal because of severe renal failure will be accordingly specified along the protocol.

¹Kidney Disease: Improving Global Outcomes (KDIGO) CKD Work Group. KDIGO 2012 Clinical Practice Guideline for the Evaluation and Management of Chronic Kidney Disease. *Kidney inter., Suppl.* 2013; 3: 1–150.; 2ADENURIC® SmPC, Appendix II:EU SmPCs for Adenuric®.

2. Protocol changes in detail

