Report specific changes for relevant protocol section (including paragraph number and pages), additions should be highlighted as underlined, whereas deletions as ~~strike-out~~, reporting whenever possible the full affected changes. Alternatively, the tracked changes can be strictly limited to the affected lines.

▪ Amendment to Protocol Section 2 and Section 8:

Current version (page 4/18 and 45/72):

Section 2 Protocol Synopsis Exclusion Criteria (page 7) and Section 8.3.2 Exclusion Criteria (page 49) is amended as described below:

...

- patients with severe renal insufficiency~~;~~, as defined below calculated based on local clinical practice:
 - adult patients with a clearance creatinine < 30 mL/min;
 - pediatric patients with eGFR <60 mL/min/1.73 m².

...

Section 8.3.3 Withdrawal of patients from therapy or assessment (page 49/50) is amended as described below:

....

Patients should not receive further study medication and will be withdrawn from the study (study termination) in case of medical emergency or necessity including but not limited to:

- adverse events with a possible, probable or certain drug-causality as per Investigator's judgment of severity grade ≥ 3 CTCAE version 4.03;
- appearance of skin rash or of any signs which may indicate allergic/hypersensitivity reactions (**NOTE**: in case of severe allergic/hypersensitivity reactions, febuxostat must not be re-started in patients at any time; for guidance please refer to the EU SmPC, Appendix II:TLS Risk Assessment);
- severe hepatic insufficiency;
- severe renal insufficiency;
NOTE: renal insufficiency defined as below:
 - adult patients with a clearance creatinine < 30 mL/min;
 - pediatric patients with eGFR < 60 mL/min/1.73 m².

.....

SIGNATURES

The signatories have read the clinical trial protocol amendment No. 2 dated 03 Feb 2017 to the clinical trial protocol titled "*Open label, multi-centre, parallel group study to compare the pharmacokinetics (PK), pharmacodynamics (PD) and safety of febuxostat between pediatric patients ($\geq 6 < 18$ years of age) and adults*" - Final Version 1.0, dated 12 Apr 2016 - carefully and agree to adhere to its provisions.

SPONSOR's Representative

Signature

Date

Co-ordinating Investigator

PRINCIPAL INVESTIGATOR'S STATEMENT

a) Clinical Statement

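### Table 3 lists Cockcroft-Gault as the only estimated renal parameter, with no age limit, although 96 of 120 planned patients are under 18

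*Combined protocol and SAP*

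**What the plan says.** Section 8.6.3.3 describes the local safety laboratory tests and lists the analytes in Table 3. Measured creatinine and BUN/urea are among them. Under a separate heading for estimated parameters there is a single line, "CLcr calculation according to Cockcroft and Gault formula", with nothing to limit it to adults. Non-Substantial Amendment No. 1 revises and reprints Table 3 and leaves this line as it was. The visible text names no paediatric estimating equation anywhere.

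Substantial Amendment No. 2 treats adults and children differently. For adults, its reasons section says that "severe renal insufficiency (grade 4) corresponds to creatinine clearance" below 30 mL/min. It continues: "For the pediatric population a more conservative approach is commonly applied, and it considers the corrected creatinine clearance with the cut off" at 60 mL/min/1.73 m². The amended exclusion criterion uses the same two scales, mL/min for adults and an indexed value for the others ("pediatric patients with eGFR <60 mL/min/1.73" m²). Amendment 2 does not touch Table 3.

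Section 9.3.6 says that laboratory parameters will be summarised by dose and age group.

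**The concern.** Cockcroft-Gault was built for adults and returns a clearance in mL/min, unadjusted for body surface; this is general methodological knowledge. The trial is mainly paediatric, and its comparison runs across age groups from 6 years upwards. A renal estimate that suits only the adult group is a poor tool for following renal function in the other four cohorts, and a table of it by age group would mix body size with kidney function.

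The line is also out of step with the rest of the protocol, which adapts comparable measures to age: Lansky below 16 years and Karnofsky from 16 (section 8.6.3.5), and separate phosphorus thresholds and age-specific creatinine upper limits for the TLS diagnosis (Appendix I). At stake is the quality of renal safety monitoring and reporting in patients at risk of acute kidney injury.

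**Working it through.** **Step 1: the planned numbers.** Section 9.1 gives about 24 patients in each of five age and dose groups: 5 × 24 = 120. Section 8.1 gives 48 + 48 + 24 = 120. The plan's total reproduces. Patients under 18: 48 + 48 = 96, and 96/120 = 80%. Group sizes are approximate in the protocol, so the share is approximate too.

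**Step 2: the texts side by side.**

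| Source | Adults | Under 18 |
|---|---|---|
| Table 3 (protocol and Amendment 1) | Cockcroft-Gault, mL/min | the same line, no distinction |
| Amendment 2, reasons and exclusion criterion | creatinine clearance, mL/min | corrected clearance or eGFR, mL/min/1.73 m² |

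The one estimate listed for everybody is therefore on the scale that the sponsor uses for adults only.

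**Step 3: how far the two scales differ.** An indexed value converts to mL/min as (indexed value × body surface)/1.73. The documents give no body surface figures, so those below are assumptions. For an indexed value of 60:

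- assumed range for ages 6 to 11: 60 × 0.75/1.73 = 26.0 and 60 × 1.35/1.73 = 46.8 mL/min
- assumed range for ages 12 to 17: 60 × 1.20/1.73 = 41.6 and 60 × 1.90/1.73 = 65.9 mL/min

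The same indexed renal function thus corresponds to anything from about 26 to 66 mL/min. This illustrates why an unindexed figure says little about a child unless body size is known. It does not measure an error in this trial, because the documents never ask anyone to compare a Table 3 value with 60.

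**Step 4: where the Table 3 value is used.**

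- Clinical TLS (Appendix I) uses serum creatinine against the upper limit of normal, which is age- and sex-adjusted where the local laboratory gives none. It does not use clearance.
- Exclusion 6 and the withdrawal rule in section 8.3.3 name no formula. Amendment 2 leaves the exclusion value "as defined below calculated based on local clinical practice".
- No PK or PD endpoint in the visible text uses creatinine clearance.
- Section 9.3.6 refers to laboratory parameters in general. Whether the separately headed estimate is among them is not stated, and the synopsis list of blood safety tests, as shown in Amendment 1, does not include it.

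What remains is renal safety monitoring, and possibly safety reporting.

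**Step 5: whether a replacement is feasible.** Creatinine is already measured. A height-based equation also needs height. Section 8.6.3.2 does not list height among the vital signs. It may be part of the demographic data collected at Screening (section 8.6.1.1), and the hydration advice per m² in section 8.5.5 implies that body size is known at the site.

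**The case against.** The best reply is that nothing turns on the line. It is a derived value in a laboratory list. Investigators also see creatinine and BUN/urea at every visit, must assess out-of-range results clinically, and may order any further examination. Paediatric haematology sites can be expected to use their own estimate. Even the entry of the value into the safety tables is an inference. All of this stands and limits the point to monitoring and reporting. It does not make the line suitable for children: discretion at each site yields no common paediatric estimate, and Table 3 asks for the wrong one.

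A reader might infer that Cockcroft-Gault decides who is excluded or withdrawn for renal reasons. The documents do not say so. Neither rule names the formula, and in Amendment 2 the paediatric exclusion limit is already an indexed eGFR obtained by local practice.

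A reader might also go on to Amendment 2's scope. The numeric limits were added "As requested by the Hungarian National Institute of Pharmacy and Nutrition Agency", and the amendment is submitted to the authority, ethics committees and "Investigators involved in the study in Hungary". They apply to exclusion and, through a note ("renal insufficiency defined as below"), to withdrawal. Elsewhere exclusion 6 carries no number. For adults the product label in Appendix II partly fills the gap with 30 mL/min; no visible text gives a paediatric limit outside Hungary. This is worth noting, but the documents do not show that 60 mL/min/1.73 m² should apply everywhere. Amendment 2's reasons describe that value as marking kidney damage. Renal dysfunction raises the TLS risk category in Appendix III, so a wider limit would exclude, or stop prophylaxis in, children with moderate impairment who are at raised risk. A difference between countries also arises only if sites elsewhere read the word severe as below 30, which is an assumption.

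**Conclusion.** The point holds as a minor one. Table 3 prescribes one estimated renal parameter for all ages, it is an adult, unindexed estimate, and about 80% of planned patients are under 18. The sponsor's own account of usual paediatric practice in Amendment 2 supports the criticism.

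A reader might infer a bias in the PK, PD or clinical TLS results. The visible text gives no route for one, and none is claimed. How many children would be monitored less well because of this line cannot be estimated from the documents.

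The conclusion rests on two things: the general knowledge that Cockcroft-Gault is an adult estimate without indexing, and the reading that a line with no age limit applies to every patient. Blacked-out text could contain a use of creatinine clearance that is not visible here, so confidence in the limited consequence is moderate.

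**What to change.** In Table 3, restrict Cockcroft-Gault to adults and list, for patients under 18, a height-based paediatric eGFR in mL/min/1.73 m², for example bedside Schwartz. State in section 8.6.1.1 that height is recorded at Screening, if the eCRF does not already capture it with demographics. If the estimate is to be tabulated under section 9.3.6, show adult and paediatric values separately with their units.

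The cost is a small protocol amendment and a changed eCRF derivation. No extra patients or blood samples are needed. Extending the Hungarian limits to other countries is a separate trade-off for the sponsor and is not part of this change.

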8.6.3.5 Performance Status evaluation

Performance Status (PS) evaluation will be carried out throughout the study at each visit. The Karnofsky PS scale will be used for patients aged 16 years and older; the Lansky Play PS scale will be used for patients aged less than 16 years [34-38]. (see Appendix IV: Karnofsky and Lansky Play performance status scales).

[figure not shown]
8.6.4 LTLS and CTLS Assessment

Investigators will assess the occurrence of LTLS and CTLS based on local laboratory tests, at Visit 1 (Day 1) and then on each study visit starting from Visit 3 (Day 3) until Evaluation Visit (Visit 8, Day 8). The baseline assessment (Visit 1, Day 1) will be performed prior to the Start of Treatment in order to confirm the patient's eligibility.

Investigators will follow the Cairo and Bishop criteria reported in Appendix I: Definition of LTLS and CTLS for their evaluation; they will document the occurrence of LTLS and CLTS in patient's medical record and report it in the relevant section of the eCRF.

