8.5 TREATMENTS

8.5.1 Treatment Allocation

The study will be performed according to an open design; no blinding technique will be adopted.

Eligible patients will receive study treatment at Visit 1 (Day 1) after completing the relevant “prior to drug administration” procedures and re-checking of the eligibility criteria.

The IMP box assignment will be performed by means of the IxRS system (see section 10.1.2) without any randomized allocation. The first ≈24 children will be allocated to the 40 mg dose, the following ≈24 children to the 60 mg dose. The first ≈24 adolescents will be allocated to the 80 mg dose, the following ≈24 adolescents to the 120 mg dose. The ≈24 adults will be allocated to the 120 mg dose.

For children, the 20 mg febuxostat tablets will be used, whereas for adolescents and adults the market product ADENURIC® 80 mg and 120 mg will be employed as represented below:

Table 1. Febuxostat: Treatment dose and form

Patient Population	Treatment dose	Treatment form
Children	febuxostat 40 mg	2 tablets 20 mg
	febuxostat 60 mg	3 tablets 20 mg
Adolescents	ADENURIC® 80 mg	1 tablet 80 mg

	ADENURIC® 120 mg	1 tablet 120 mg
Adults	ADENURIC® 120 mg	1 tablet 120 mg

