9.3.4 Secondary analysis

- ***Pharmacodynamic endpoint:***

Area under plasma uric acid concentration curves (AUC sUA_{1-8}) from baseline (Visit 1, Day 1) to the Evaluation Visit (Visit 8, Day 8) will be computed for dose and age group using a trapezoidal rule which approximates the integral or the area under a curve.

A graphic example is provided in order to show which is the area considered to calculate AUC.

Figure 1

The trapezoidal rule is a numerical method to be used to approximate the integral or the area under a curve. Trapezoidal rule first involves dividing the area into a number of strips of equal width, with low limit identified with a and upper limit with b. Then, approximating the area of each strip by the area of the trapezium formed and summing these approximations, the final numerical result will be the area under the curve.

The trapezoidal rule will be presented by mean of a definite integral:

$$\int_a^b f(x)dx$$

Last observation carried forward method (LOCF) will be applied for patients who discontinued the study prematurely and a linear interpolation method will be used to impute the missing data between visits.

The pharmacodynamic analysis will be run on PK population and for exploratory reasons on ITT population.

- ***PK/PD endpoint:***

Observed exposure-response data will be descriptively and graphically summarized by age and dose group.

The aim of this analysis is to support the assumption of a comparable PK/PD relationship between pediatric patients ($\geq 6 < 18$ years of age) and adults and to evaluate if potential deviations in PK are clinically relevant.

This analysis will be conducted on the PK population.

- ***Clinical endpoints: Incidence of LTLS and CTLS***

- The assessment for LTLS from Start of Chemotherapy (Visit 3, Day 3) to the Evaluation Visit (Visit 8, Day 8) will be defined as:

1: PRESENCE 2 or more laboratory abnormalities including: a 25% increase or levels above normal for serum uric acid, potassium, and phosphate or a 25% decrease or levels below normal for calcium.

0: ABSENCE less than 2 laboratory abnormalities including: a 25% increase or levels above normal for serum uric acid, potassium, and phosphate or a 25% decrease or levels below normal for calcium.

- The assessment for CTLS from Start of Chemotherapy (Visit 3, Day 3) to the Evaluation Visit (Visit 8, Day 8) is defined as:

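### Sections 8.6.4 and 9.3.4 give two LTLS rules that are not equivalent, and the plan does not name the data source that is analysed

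*Combined protocol and SAP*

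**What the plan says.** **How the call is made (8.6.4).** "Investigators will assess the occurrence of LTLS and CTLS based on local laboratory tests", at Visit 1 before treatment to confirm eligibility and then at every visit from Visit 3 (Day 3) to Visit 8 (Day 8). On criteria: "Investigators will follow the Cairo and Bishop criteria reported in Appendix I: Definition of LTLS and CTLS for their evaluation". They are to document the occurrence in the medical record and "report it in the relevant section of the eCRF". Section 8.5.1 says of the design that "no blinding technique will be adopted".

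**What is recorded (8.6.3.3).** The safety panel covers all laboratory parameters needed for LTLS and CTLS, and "Safety laboratory results as well as clinical assessments for out of range values will be recorded in eCRF". Sites also notify the sponsor of their normal ranges. Urinalysis is the exception: only the clinical assessment is entered. It is not an LTLS input.

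**How the endpoint is coded (9.3.4).** One value per patient for Day 3 to Day 8: "1: PRESENCE 2 or more laboratory abnormalities including: a 25% increase or levels above normal for serum uric acid, potassium, and phosphate", with the mirror condition for calcium. CTLS is this LTLS plus renal insufficiency, arrhythmia, sudden death or seizure. Incidences are compared by dose and age group with a chi-square test on the ITT population.

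**What Appendix I adds.** Its table fixes limits: uric acid at least 8 mg/dL, potassium at least 6.0 mmol/L, phosphorus at least 1.45 (adults) or 2.1 mmol/L (children), calcium at most 1.75 mmol/L, or a 25% change from baseline. Adolescents take the adult phosphorus limit. For CTLS the renal criterion is creatinine at least 1.5 times ULN, with fallback ULNs by age and sex.

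**The concern.** The same endpoint is described twice, and the two descriptions can classify the same patient differently. The plan does not choose between them, nor between the investigator's entry and a derivation from laboratory values. Each choice has its own weakness.

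- **If 9.3.4 is run literally on eCRF values,** two abnormalities on different days can make a case. So can values outside a local normal range that do not reach the Appendix I limits.
- **If the investigator's call is analysed,** the rule is applied separately at approximately 40 sites. It has four analytes, each with a level limit and a 25% change, a phosphorus limit that depends on age, and creatinine ULNs that depend on age and sex. The plan describes no step that re-applies the rule.

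With very few cases per cohort, either route can change the incidences that the age and dose comparison rests on.

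**Working it through.** **The plan's own figure.** 5 groups × 24 = 120 treated; 120 / 0.90 = 133.3, so 134 to screen, against approximately 135 stated in 9.1. This reproduces, and the point does not depend on it.

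**The two rules side by side**

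| | 8.6.4 with Appendix I | 9.3.4 as worded |
|---|---|---|
| Unit | each visit | one value, Days 3–8 |
| Level limit | fixed cut-offs (table) | above or below normal |
| Timing of the two abnormalities | assessed per visit; Appendix I itself is silent | not stated |
| Renal criterion for CTLS | creatinine ≥ 1.5 ULN | renal insufficiency, no number |

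Two hypothetical patients separate them.

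- **Patient A** has potassium over its limit on Day 3 only and calcium under its limit on Day 8 only. A per-visit call never sees two abnormalities together; 9.3.4 read literally counts a case.
- **Patient B** has, at one visit, potassium above the local ULN but under 6.0 mmol/L and uric acid above the local ULN but under 8 mg/dL, neither up by 25%. The Appendix I table gives no case; 9.3.4 does. Patient B requires local ULNs below those cut-offs, and the documents give no local ranges.

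**Weight of one case.** FLORENCE LTLS incidence on febuxostat 120 mg is 8.1% (120 mg SmPC section 5.1, in Appendix II). Expected per cohort: 0.081 × 24 = 1.94. One patient: 1/24 = 4.2 percentage points, and 4.2 / 8.1 = 0.52, about half the expected incidence.

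**Number of assessments in the endpoint window.** 6 visits × 120 patients = 720. The Visit 1 assessment serves eligibility and is not part of the endpoint. This is a count of opportunities, not an error rate; the documents give none.

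**Cross-day counting, under assumptions.** The documents give no daily abnormality rates. Let q be the daily probability of abnormality per analyte, with four independent analytes, six independent days, and the same-visit rate set to 8.1%:

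- Same visit: 1 − (1 − P[Bin(4, q) ≥ 2])^6 = 0.081 gives q = 0.0499.
- Over the window: Q = 1 − (1 − 0.0499)^6 = 0.265, and P[Bin(4, Q) ≥ 2] = 0.287.

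The window rule then gives about 28.7%, or 0.287 × 24 = 6.9 cases against 1.9. Independent days are the extreme. In a two-state Markov model, let s be the chance that an abnormal value is still abnormal next day, recalibrated to 8.1% same-visit:

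| s | Window rule | Cases per 24 |
|---|---|---|
| independent days | 28.7% | 6.9 |
| 0.5 | about 17% | about 4 |
| 0.8 | 10.9% | 2.6 |
| 0.95 | 8.5% | 2.0 |

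Letting the analytes correlate as well (latent Gaussian model, same-visit rate again 8.1%), the window rule gives:

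| Between-analyte correlation | Day-to-day 0 | 0.5 | 0.8 | 0.95 |
|---|---|---|---|---|
| 0 | 29% | 22% | 15% | 10% |
| 0.3 | 15% | 13% | 11% | 9% |
| 0.6 | 10% | 10% | 9% | 9% |

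**Investigator's call, under assumptions.** With per-visit specificity sp, the false-positive rate over six visits is 1 − sp^6: 0.6% at 99.9%, and 5.9% at 99%. With sensitivity 0.9 the observed incidence is 0.081 × 0.9 + 0.919 × (1 − sp^6). This is 7.8% at sp = 99.9% and 12.7% at 99%, so miscalls can lose cases as well as add them.

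**The case against.** **Section 9.3.4 may mean the per-visit assessment.** It opens by speaking of the assessment for LTLS, and 8.6.4 and the flow chart schedule that assessment visit by visit. It can be read as summarising those calls over the window. The lead sentence of Appendix I also speaks of values outside normal, so 9.3.4 may be shorthand for the table beneath it. This is fair. A reader might infer that abnormalities from different days will be counted as events. The plan does not say so: 9.3.4 is silent on timing and does not instruct pooling. What stands is that the wording permits that reading and differs from the Appendix I table.

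**The two mechanisms do not add up.** Miscalls matter if the investigator's entry is analysed; cross-day and sub-limit counting matter if 9.3.4 is run on laboratory values. This also stands. The defect is that the source and the timing condition are not named.

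**There are safeguards.** Section 10.2 provides electronic checks, queries and medical review before lock, and 10.4.1 provides 100% source data verification. These compare entries with source and query discrepancies; nothing in them says the LTLS rule is re-applied. Section 9.5 leaves endpoint detail to a SAP finalised before database lock. No such text is visible here, and that or redacted text may settle the matter.

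**Bias from open treatment is limited.** Every patient receives febuxostat and the LTLS rule is numerical, so only age and dose contrasts could be affected. A reader might go further and suppose that adult and paediatric patients have separate care teams, so that errors line up with age. The documents do not say this, nor do they say how investigators apply the criteria in practice.

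**The comparison is weak in any case.** With 24 against 24 and an assumed two-sided 5% level, power to detect 8.1% against 16.2% is about 13%. The incidences will mainly be read descriptively, which lowers the stake but still requires one definition.

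**Conclusion.** The point holds as a gap in endpoint definition. Sections 8.6.4 with Appendix I and 9.3.4 are not equivalent, and the visible text names neither the analysed source nor the timing condition. One misclassified patient is worth 4.2 points in a cohort expected to have about 1.9 cases. That rests on carrying the adult FLORENCE rate to all five groups, which is an assumption for children and adolescents.

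The size of any cross-day inflation cannot be known from the documents. Against a same-visit 8.1%, it runs from negligible (about 8.5%) to large (about 29%) with independent analytes. At a between-analyte correlation of 0.6 it is only about 9% to 10%. The upper figure needs independence across both days and analytes, which the documents do not support, and should not be quoted as an expected effect. The effect of sub-limit values depends on local ranges and was not quantified. The endpoint is secondary; the 120 patients and the primary PK analysis are untouched. It is worth correcting because correction is cheap and uses values already collected.

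**What to change.** In 9.3.4 or the SAP:

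1. Reconcile the wording with Appendix I so that one set of limits defines LTLS, and replace unqualified renal insufficiency with the Appendix I creatinine criterion.
2. Derive LTLS by program from the recorded local values, scheduled and unscheduled (8.6.3.3 allows extra sampling at any time), with Visit 1 as baseline and the age-specific phosphorus limits. Count a case only when two abnormalities occur at the same visit or in the same sample.
3. Derive CTLS and its grade from the derived LTLS plus recorded creatinine relative to ULN and reported arrhythmia, seizure or sudden death. The clinical components still depend on reporting; laboratory data alone cannot supply them.
4. Make the derived variables the analysed endpoint, keep the investigator's call as a supportive analysis, and list discordant patients.

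The cost is SAP wording and a short program, with no new data. Section 9.5 allows changes that do not touch the primary endpoint or analysis to be detailed in the SAP before lock. The one downside is that Appendix I contains no same-visit condition, so it must be declared as an added specification.
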